## **7.5. Selection of Study Population**

The Investigator should keep a subject-screening log of all potential subjects who consented and were subjected to screening procedures.

Subjects who fail to meet the inclusion criteria or meet any exclusion criterion should not, under any circumstances, be randomized into the study. There can be no exceptions to this rule.

This study will be conducted in male and female subjects. The study may not necessarily be balanced regarding gender. The study was not formally powered to detect differences between genders for the primary endpoint. It is not planned to perform sub-analyses on gender.

### **7.5.1. Inclusion Criteria**

For inclusion in the study, subjects should fulfill the following criteria:

1. Provision of signed and dated, written informed consent prior to any study specific procedures.
2. Healthy male and/or female subjects of non-child-bearing potential aged 18 to 55 years (inclusive) with suitable veins for cannulation or repeated venipuncture.
3. Females must have a negative pregnancy test at screening and on admission to the unit, must not be lactating and must be of non-child-bearing potential, confirmed at screening by fulfilling one of the following criteria:
  - 3.1. Post-menopausal defined as amenorrhea for at least 12 months or more following cessation of all exogenous hormonal treatments and FSH levels in the post-menopausal range.
  - 3.2. Documentation of irreversible surgical sterilization by hysterectomy, bilateral oophorectomy or bilateral salpingectomy but not tubal ligation.
4. All male subjects who are sexually active must agree to use a highly effective contraception form of birth control in combination with a barrier method from the first dose of IMP until 16 weeks after the study End-of-Treatment visit.
5. Have a BMI between 18 and 29.9 kg/m^2 inclusive and weigh at least 55 kg and no more than 100 kg inclusive.
6. Only applicable to the PAREXEL Early Phase Clinical Unit Berlin: Able to understand, read and speak the German language.

### **7.5.2. Exclusion Criteria**

Subjects will not enter the study if any of the following exclusion criteria are fulfilled:

1. History of any clinically significant disease or disorder which, in the opinion of the Investigator, may either put the subject at risk because of participation in the study, or influence the results or the subject's ability to participate in the study.
2. History of severe allergy/hypersensitivity or ongoing allergy/hypersensitivity, as judged by the Investigator or known history of allergy or reaction to any component of the investigational product formulation.
3. History of anaphylaxis to any biologic therapy.
4. A helminth parasitic infection diagnosed within 24 weeks prior to the date informed consent is obtained that has not been treated with, or has failed to respond to standard of care therapy.
5. Acute upper or lower respiratory infections requiring antibiotics or antiviral medication within 30 days prior to the date informed consent is obtained or during the screening period.
6. Any disorder, including, but not limited to, cardiovascular, gastrointestinal, hepatic, renal, neurological, musculoskeletal, infectious, endocrine, metabolic, hematological, psychiatric, or major physical impairment that is not stable in the opinion of the Investigator and could:
  - 6.1. Affect the safety of the subject throughout the study.
  - 6.2. Influence the findings of the studies or their interpretations.
  - 6.3. Impede the subject's ability to complete the entire duration of study.
7. Any clinically significant abnormal findings in physical examination, vital signs, hematology, clinical chemistry, or urinalysis during screening, which in the opinion of the Investigator, may put the subject at risk because of his/her participation in the study, or may influence the results of the study, or the subject's ability to complete entire duration of the study.
8. Alanine aminotransferase (ALT) or aspartate aminotransferase (AST) level  $\geq 1.5$  times the upper limit of normal (ULN) confirmed during screening period.
9. White blood cell count and neutrophils  $<$  lower limit of normal.
10. Any clinically significant illness, medical/surgical procedure, or trauma within 4 weeks of the first administration of IMP.

11. Any positive result on screening for serum hepatitis B surface antigen or anti-HBc antibody, hepatitis C antibody, and human immunodeficiency virus (HIV) antibody. Subjects with a history of hepatitis B vaccination without history of hepatitis B are allowed to enroll.
12. Known or suspected history of alcohol or drug abuse or excessive intake of alcohol as judged by the Investigator.
13. Has received another new chemical entity (defined as a compound which has not been approved for marketing) within 3 months of the first administration of investigational product in this study. The period of exclusion begins 3 months after the final dose or 1 month after the last visit whichever is the longest.  
*Note: subjects consented and screened, but not randomized in this study or a previous Phase I study, are not excluded.*
14. Plasma donation within 1 month of screening or any blood donation/loss more than 500 mL during the 3 months prior to screening.
15. Receipt of immunoglobulin or blood products within 30 days prior to the date informed consent is obtained.
16. Receipt of any marketed (e.g., omalizumab, mepolizumab etc.) or investigational biologic within 4 months or 5 half-lives prior to the date informed consent is obtained, whichever is longer.
17. Receipt of live attenuated vaccines 30 days prior to randomization on Day 1.
18. History of Guillain-Barré syndrome.
19. Current smokers or those who have smoked or used nicotine products including e-cigarettes within the 3 months prior to screening, as judge by the Investigator.
20. Current malignancy, or history of malignancy except for:
  - Subjects who have had basal cell carcinoma, localized squamous cell carcinoma of the skin or in situ carcinoma of the cervix are eligible provided that the subject is in remission and curative therapy was completed at least 12 months prior to the date informed consent was obtained.
  - Subjects who have had other malignancies are eligible provided that the subject is in remission and curative therapy was completed at least 5 years prior to the date informed consent was obtained.
21. Positive screen for drugs of abuse, of alcohol at screening or on admission to the study unit.
22. Use of drugs with enzyme-inducing properties such as St John's Wort within 3 weeks prior to the first administration of IMP.

23. Use of any prescribed or non-prescribed medication including antacids, analgesics (other than paracetamol/acetaminophen), herbal remedies, mega-dose vitamins (intake of 20 to 600 times the recommended daily dose) and minerals during the 2 weeks prior to the first administration of IMP or longer if the medication has a long half-life  
*Note: Hormonal replacement therapy is not allowed for females.*
24. Involvement of any AstraZeneca, PAREXEL or study site employee or their close relatives.
25. Subjects who have previously received benralizumab.
26. Judgment by the Investigator that the subject should not participate in the study if they have any ongoing or recent (i.e., during the screening period) minor medical complaints that may interfere with the interpretation of study data or are considered unlikely to comply with study procedures, restrictions, and requirements.
27. Vulnerable subjects, e.g., kept in detention, protected adults under guardianship, trusteeship, or committed to an institution by governmental or juridical order.

### **7.5.3. Discontinuation Individual Stopping Criteria and Withdrawal from the Study**

Subjects will be discontinued from the study in the following situations:

- Healthy subject decision. The healthy subject is at any time free to discontinue treatment, without prejudice to further treatment.
- Severe noncompliance to study protocol.
- Any significant and clinically relevant changes in the safety parameters (e.g., ECG, BP, pulse rate, laboratory assessments and AEs).
- Study specific withdrawal criteria: If a subject reports symptoms, which are considered unacceptable by the subject or the Investigator, he/she will be withdrawn from the study. In particular:
  - Any other severe or serious adverse event (SAE) that is judged as possibly related to the IMP by the Investigator
  - Any case of Potential Hy's Law (PHL) according to [Appendix 15.3](#)

The appropriate AE form in the case report form (CRF) is to be completed.

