## 7. OVERALL DESIGN AND PLAN OF THE STUDY

### 7.1. Overall Study Design

This study will be a multicenter, randomized, open-label, parallel group Phase 1 study designed to compare benralizumab PK exposure in healthy subjects following single SC administration of fixed 30 mg dose of benralizumab by using APFS and single-use AI. Eligible subjects will be healthy subjects aged 18 to 55 years, with a body weight of 55 to 100 kg and a body mass index (BMI) of 18 to 29.9 kg/m^2. A total of 180 subjects will be randomized. Randomization will be stratified by weight group (55 to 69.9 kg, 70 to 84.9 kg and 85 to 100 kg), and within each of the 3 weight groups, subjects will be randomized 1:1:1:1:1:1 to 1 of the 6 combinations of treatment (APFS or AI) with injection site (upper arm, abdomen or thigh), presented in [Table 1](#). This study will be performed at 2 study centers.

**Table 1 Design of a Pharmacokinetic Comparability Study in Healthy Subjects for Benralizumab Accessorized Pre-Filled Syringe and Autoinjector Devices**

Number of Subjects		APFS			AI			Total
		Upper Arm	Abdomen	Thigh	Upper Arm	Abdomen	Thigh	
Body Weight	55.0 to 69.9 kg	10	10	10	10	10	10	60
	70.0 to 84.9 kg	10	10	10	10	10	10	60
	85.0 to 100.0 kg	10	10	10	10	10	10	60
Total		90			90			180

AI: Autoinjector; APFS: Accessorized pre-filled syringe device

The study will comprise of:

- A screening period of maximum of 28 days,
- One treatment period during which subjects will be resident from the day before dosing (Day -1) until 2 hours after dosing on Day 1. The subjects will then return to the center for ambulant visits on Days 2, 4, 5, 6, 8, 15, 29 and 43, and
- An End-of-Treatment visit on Day 57 (Week 8).

After a screening period of up to 28 days, eligible subjects will be admitted to the unit on Day -1 (1 day before dosing) to reassess their eligibility. Subjects who meet eligibility criteria will be randomized on Day 1 to receive a single dose of 30 mg benralizumab by either APFS or AI device. The study will be completed after the End-of-treatment visit on Day 57 (Week 8).

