## 7.2. Schedule of Assessments

The schedule of assessments displaying assessments/tasks and time points is presented in [Table 2](#).

**Table 2** Schedule of Assessments

	Screening Day -28 to -2	Day -1	Days 1 to 57
Informed consent	X		
Inclusion/exclusion criteria	X	X	
Height	X		
Weight	X	X	
Other demographic data	X		
Medical history	X		
Urinary drug and alcohol screen	X	X	
Serum pregnancy and FSH test	X		
Urine pregnancy test (dipstick)		X	Day 57
Serology	X		
Randomization			Day 1
Study residency:			
Check-in		X	
Check-out			Day 1 (2 h post-dose)
Non-residential visit	X		Days 2, 4, 5, 6, 8, 15, 29, 43 and 57
IMP (Benralizumab) administration:			Day 1 (0 h)
Safety and tolerability:			
Adverse event questioning			Pre-dose and 2 h post-dose (Day 1), Days 2, 4, 5, 6, 8, 15, 29, 43 and 57
Vital signs	X	X	Pre-dose and 2 h post-dose (Day 1), Days 2, 4, 5, 6, 8, 15, 29, 43 and 57
12-lead electrocardiogram	X		Days 1, 29 and 57
Clinical laboratory evaluations	X	X	Days 8, 29 and 57
Physical examination	X	X(brief)	Days 8, 29 and 57 (2 h post dose (brief))
Pharmacokinetics			
Serum benralizumab concentration a			Pre-dose (Day 1), Days 2, 4, 5, 6, 8, 15, 29, 43 and 57
Immunogenicity			
ADA			Pre-dose (Day 1), Days 29 and 57

ADA: anti-drug antibody; FSH: follicle-stimulating hormone; IMP: investigational medicinal product

a Samples to determine serum Benralizumab concentrations will be collected at consistent times across the different study days.

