### **8.9.3. Procedures for Handling Incorrectly Randomized Subjects**

Subjects who fail to meet the inclusion criteria or meet any exclusion criterion should not, under any circumstances, be randomized into the study. There can be no exceptions to this rule.

Where a subject, who does not meet the selection criteria, is randomized in error and this is identified before dosing, the subject should be withdrawn from the study.

If a subject, who does not meet the selection criteria, has been dosed before the error is identified, the subject should be advised to continue safety assessments to ensure their safety.

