6.1.5 Immunogenicity Variables

Anti-drug Antibody (ADA) sampling will be collected at the following time points: Day 1 pre-dose, Day 29 and 57. A sample is defined as positive if the reported titer is 50 or above.

For each subject, the following responses variables will be evaluated:

- ADA positive at any visit (at baseline and/or post-baseline)
- ADA positive at both baseline and post-baseline
- ADA positive at post-baseline only
- ADA positive at baseline only

At the study level, a subject's ADA status will be defined as being ADA positive if a positive ADA result is available at any time (including baseline or any post-baseline measurements); otherwise a subject's ADA status will be defined as ADA negative.

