6.2.3 Pharmacokinetic Analysis Set

All subjects who received benralizumab and from whom PK blood samples are assumed not to be affected by factors such as protocol violations (e.g., disallowed medications or incomplete dose administration) and who had at least one quantifiable serum PK observation post first dose will be included in the PK analysis dataset. All PK tabulations and figures will be based on the PK analysis set.

Statistical Analysis Plan

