6.3.10 Immunogenicity Analysis

ADA results will be listed by treatment (device), subjects study ADA status with positive study status first and then subjects with negative study status, subject identifier, and visit including ADA titer and eosinophil count [Appendix 16.2.6.3].

ADA responses observed during the study, as specified in Section 6.1.5, will be summarized by treatment (device) and overall [Table 14.2.4.2]. ADA positive and negative status will be summarized by visit, treatment (device) and overall [Table 14.2.4.1].

Statistical Analysis Plan

The hypersensitivity reported on treatment period will be presented by preferred term for ADA status [Table 14.2.4.3].

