6.3.11.1 Adverse Events

All AEs will be coded using MedDRA vocabulary, and will be listed by treatment (device) for each subject. A Treatment-emergent adverse event (TEAE) is defined as an AE with onset (start date/time) after dosing.

AEs will be assigned to the treatment period or pre-treatment as follows:

- Pre-treatment: All AEs with start date/time prior to dosing.
- Treatment period: AEs with start date/time at the time of or after dosing until the final visit.

The following listings will be included:

- MedDRA coding, including MedDRA lowest level term; PT and SOC [Appendix 16.2.7.1].
- Onset and resolution, including pre-treatment AE, PT, verbatim term, date of onset and resolution and time from IMP [Appendix 16.2.7.2].
- Relationship and causality, including PT, verbatim term, severity, action taken, outcome, causality, SAE and withdrawn [Appendix 16.2.7.3].
- Table of Key Information listing AEs leading to death [Table 14.3.2.1].
- Table of Key Information listing SAE [Table 14.3.2.2].
- Table of Key Information listing AEs that led to discontinuation from study (DAE) [Table 14.3.2.3].
- Table of Key Information listing for AEs associated with device malfunction [Table 14.3.2.4].
- Table of Key Information listing for AEs associated with injection site reactions [Table 14.3.2.5].

All key information listings for AEs will display the baseline eosinophil count and the subject ADA status.

Tabulation of subject counts

A summary (n and percentage) of subjects with at least one AE per category, including AEs with outcome death or discontinuation and SAEs will be presented by treatment (device) and overall [Table 14.3.1.1].

Adverse events subject based, will be summarized by treatment (device) and overall, by SOC and PT. The overall summary will additionally be by pre-treatment and treatment period respectively [Tables 14.3.1.2.1 - 14.3.1.2.2].

Causality of AE will be summarized by treatment (device) and overall, by PT [Table 14.3.1.3]. Maximum intensity of AE will be summarized by treatment (device) and overall by PT [Table 14.3.1.4].

Adverse events associated with injection site reactions will be summarized by subject counts and percentages, by treatment (device), administration site and PT [Table 14.3.1.5].

Tabulation by episode count

A summary of the number of episodes by categories, including AEs with outcome death or discontinuation and SAEs will be presented by treatment (device) and total [Table 14.3.1.6].

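### Protocol 7.5.3 takes dosed subjects off study for safety triggers after the only dose, which on its natural reading ends their scheduled ADA, safety and late PK visits

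*Protocol*

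**What the plan says.** Protocol 7.1 has each subject "randomized on Day 1 to receive a single dose of 30 mg benralizumab by either APFS or AI device". No further dose is given.

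Protocol 7.5.3 opens with "Subjects will be discontinued from the study in the following situations". Its safety triggers are clinically relevant changes in safety parameters, severe or serious events that the investigator thinks possibly related to the product, and any Potential Hy's Law case. The section does not say whether a dosed subject keeps any scheduled visit, and Table 2 has no early-termination visit.

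For ADA, Table 2 gives the draws as "Pre-dose (Day 1), Days 29 and 57". SAP 6.1.5 calls a subject positive if any sample is positive, baseline included; otherwise the subject's "ADA status will be defined as ADA negative". That status is used in two places:
- SAP 6.3.10: "The hypersensitivity reported on treatment period will be presented by preferred term for ADA status".
- SAP 6.3.11.1: "All key information listings for AEs will display the baseline eosinophil count and the subject ADA status". One of these listings covers events that led to discontinuation from the study.

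Protocol 8.9.3 deals with a different group, subjects found to be ineligible after dosing. There, "the subject should be advised to continue safety assessments to ensure their safety".

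**The concern.** In a repeat-dose trial, a safety stopping rule protects the subject by preventing the next dose. Here there is no next dose. Once the injection is given, taking the subject off study leaves exposure unchanged and can only shorten observation.

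The subjects affected are those with a safety signal. Safety and immunogenicity are both secondary objectives (Protocol 6.2), and Protocol 11.11 undertakes to examine ADA against safety and hypersensitivity. A subject with a severe, possibly related hypersensitivity reaction in the second week meets a trigger before any post-dose ADA sample is due. With a negative baseline, that subject then appears as ADA negative in the hypersensitivity table, although never tested after dosing. For any such subject who would have tested positive, the table understates the association it is meant to show.

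**Working it through.** **1. Scheduled samples lost.** Inputs are the rows of Table 2 in Protocol 7.2. Post-dose PK falls on Days 2, 4, 5, 6, 8, 15, 29, 43 and 57 (9 samples), post-dose ADA on Days 29 and 57 (2), and post-dose laboratory tests on Days 8, 29 and 57 (3). Counting the draws after the last visit attended:

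| Last visit | ADA lost | Laboratory lost | PK lost |
|---|---|---|---|
| Day 8 | 2 of 2 | 2 of 3 | 4 of 9 |
| Day 15 | 2 of 2 | 2 of 3 | 3 of 9 |
| Day 29 | 1 of 2 | 1 of 3 | 2 of 9 |
| Day 57 | 0 | 0 | 0 |

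**2. What follows for ADA status.** Take a subject with a negative baseline who stops after Day 8. No positive result exists, so the default in SAP 6.1.5 gives ADA negative. The hypersensitivity table and key listings use this subject-level status. The by-visit ADA table and the subject listing in SAP 6.3.10 would show that the Day 29 and Day 57 results are absent.

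**3. What survives a stop.**
- Protocol 12.2.2: unresolved events are followed clinically, but that follow-up is not entered in ClinBase; the sponsor may ask for more information.
- Protocol 12.3: SAE reporting continues.
- Appendix 15.3: Potential Hy's Law cases have liver monitoring, work-up and dedicated CRF modules.

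None of these provides for an ADA or PK draw.

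**4. Primary comparison, as a check on size only.** The plan's own figure first. At 50% CV, sigma = sqrt(ln(1 + 0.5²)) = 0.472. With limits 0.80 to 1.25, two one-sided 5% tests and a true ratio of 1 (assumed; the plan states none), power is 82.2% at 81 per arm. So 162 evaluable meets the 80% target, and 162/0.9 = 180. At 90 per arm power is 86.9%.

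The PK analysis set takes dosed subjects whose samples are not thought to be affected by violations and "who had at least one quantifiable serum PK observation post first dose will be included in the PK analysis dataset". A shortened AUClast can therefore enter the ANOVA unless the data review meeting removes it. To size this, assume one compartment, an absorption half-life of 3 days and an elimination half-life of 10 to 20 days (none of these is in the documents). With t = visit day minus 1:

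F(t) = 1 − (ka·e^(−ke·t) − ke·e^(−ka·t))/(ka − ke), and r = F(t)/F(56).

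For a Day 8 stop, r = 0.212, 0.160 and 0.135 at elimination half-lives of 10, 15 and 20 days. One such subject among 90 lowers that arm's geometric mean by 1 − r^(1/90), which is 1.7%, 2.0% and 2.2%. In 60,000 simulated trials of the planned ANOVA at 50% CV, power was 86.8% with no stops and 82.6% to 84.4% with one Day 8 stop in one arm. With one Day 15 stop it was 85.7% to 86.5%. Modelled concentration at Day 15 is 0.81 to 0.98 of that at Day 8, so under these assumptions Cmax is unaffected by a stop at Day 8 or later.

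**The case against.** The strongest reply is that no sentence says visits stop. The wording of 7.5.3 is loose: its first bullet speaks of stopping treatment, and several triggers turn on judgement. When medication is required, Section 8.7 has the investigator, after consulting the sponsor's lead physician, decide whether the subject continues. Section 11.2 also uses all captured data unless consent is withdrawn. This stands in part. The end of visits is an inference from discontinuation from the study combined with the absence of retention wording, and Section 8.7 is a real exception. But Section 11.2 governs data already captured and does not require a visit.

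Ending participation also has a protective side. It releases an unwell volunteer from venipuncture, dietary limits and a near-total medication ban. That is fair, and it is why any retention should be a request that leaves room for consent and clinical judgement.

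The comparison with 8.9.3 is limited, because that section covers safety assessments only and not ADA or PK. It shows that the protocol keeps one group of dosed subjects under observation; it is not a precedent for the full schedule.

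The ADA default is a separate weakness. It also catches subjects who withdraw consent or miss visits, so changing 7.5.3 alone would not cure it.

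A reader might go further and infer that safety follow-up ceases altogether. The documents do not support that, since SAE reporting, clinical follow-up of events and Potential Hy's Law monitoring all continue.

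**Conclusion.** The point holds as a low-priority design improvement. Following 7.5.3 as written most naturally ends scheduled ADA, safety and late PK sampling in dosed subjects with a safety signal, with no reduction in exposure in return. A subject stopped before Day 29 loses both post-dose ADA samples and, if negative at baseline, is reported as ADA negative in the outputs that relate ADA to safety. The by-visit ADA outputs would still reveal the gap. For Potential Hy's Law cases the laboratory loss is smaller than the table suggests, because liver data are still collected.

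The documents give no event rate. The number affected is unknown and, in healthy volunteers given one dose, probably low.

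A reader might also infer that the device comparison is biased or underpowered. That should not be relied on. The effect is small, it rests on PK values absent from the documents, and the data review meeting may exclude a shortened profile. Simulated power falls below 80% (to between 76% and 79%) only if Day 8 stops, one in either or both arms, come on top of the full 10% dropout already allowed for. The 162 and 180 stand.

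**What to change.** In Protocol 7.5.3, state that a dosed subject who meets a safety criterion is asked to complete the scheduled safety, ADA and PK visits to Day 57, recorded in ClinBase, unless consent is withdrawn or the investigator judges it unsafe. State also that subjects retained in this way are not deviations under SAP 6.3.6, which lists meeting discontinuation criteria without being discontinued as a deviation type.

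Separately, in SAP 6.1.5, class a subject with no post-dose ADA sample and no positive baseline as not evaluable, and carry that category into the hypersensitivity table and key listings. This also covers early leavers for other reasons.

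The cost is a protocol amendment, with ethics and regulatory approval as appropriate under Section 3.6, a SAP update, and some continued visit burden for the subject. The visits are already in Table 2. The PK gain is not assured, because medication given for the event may take a subject's samples out of the PK set; the ADA and safety data would still be gained.
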